**VOICE THERAPY WITH A SEMI-OCCLUDED VOCAL TRACT:
FROM CURRENT CHALLENGES TO NEXT LEVEL EFFICACY STUDIES**

Protocol and statistical analysis plan

Document date: March 3, 2023

PROTOCOL

This study has been approved by the Ethics Committee of Ghent University Hospital (BC-09807).

Participants

Female students in the first year of study toward a bachelor degree in Logopaedic and Audiological Sciences at Ghent University (academic year 2021-2022), will be recruited for this study by convenience sampling. They will all provide written informed consent. Exclusion criteria are: an organic vocal fold pathology diagnosed by a specialized otorhinolaryngologist, smoking, pregnancy and hearing problems.

Design

A randomized controlled trial will be used. Participants will be assigned randomly to one of three experimental groups or a control group: (1) straw phonation (SP) in air, (2) SP in 2cm water, (3) SP in 5cm water or (4) /u/ phonation with similar soft onset and slightly pursed lips as in SP but without a straw (control group). An online random number generator will be used for this procedure.

Material and methods

Straw phonation material

Ecologic compostable wheat stirring straws with a diameter of 3mm and a length of 20cm will be selected for all experimental groups. SP in water will be performed in reusable cups, and the water depth (2cm or 5cm) will be set by drawing a line on the straw.

Preparatory phase

Before the experiment, in the second week of the academic year, all students will receive one group SP workshop of 20 min guided by an experienced voice therapist ([name]). The aim of this session is to strive for a correct and comfortable SOVT production prior to the actual experiment. First, focus will be on an eutonic posture in sitting position and costo-abdominal breathing. Participants will be instructed to breath in through the nose and blow out through the mouth without phonation. Second, they will be asked to repeat this but now adding phonation on a [ɔ] vowel with soft onset [hhhɔɔɔ] during exhalation, at habitual comfortable pitch and loudness. Afterwards, both step one (without phonation) and step two (with phonation) will be repeated with the straw. Attention will be drawn to sensory feedback, forward focus, and avoidance of hyperfunction. At the preparatory phase, students will be unaware of their group assignment and will be specifically instructed to not practice the exercises at home.

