Flexible strobovideolaryngoscopy and phonatory tasks

In the third and fourth week of the academic year, all students will undergo flexible SVL by a specialized otorhinolaryngologist ([name] or [name]) using an EndoFLEX Spectar laryngoscope (Xion Medical). The participants will be examined in seated position with the head upright and without administration of topical anesthesia. During the examination, they will be asked to phonate an [u] vowel at habitual pitch and loudness (baseline), followed by the specific SOVT exercise of their group assignment. For the SOVT phonation, they will be instructed to produce an [u] vowel at habitual pitch and loudness with soft onset and slightly pursed lips through the stirring straw (either in air, 2cm water or 5cm water) or without a straw (control group). The [u] vowel will be selected for all phonatory tasks (baseline and SOVT, both in the experimental group and the control group) so that potential differences are more certainly attributable to SP and not to differences in vowel production. The same voice therapist ([name]) will guide them through these phonatory tasks, together with a master's student ([name]) for practical support.

Visual-perceptual ratings

After data collection, all video samples will be evaluated randomly and blindly by an otolaryngology resident ([name]) and a speech-language pathologist specialized in voice ([name]). Evaluations will be standardized by use of the Voice-Vibratory Assessment with Laryngeal Imaging (VALI) rating form for stroboscopy (Poburka et al., 2017). In advance, a half hour training session will be provided in which each parameter will be clarified with the definition, a high-quality graphic, and two video examples.

After the training, the assessors will first independently evaluate each video sample on a self-paced basis, after which a consensus evaluation will be reached. Ten percent of the samples will be randomly repeated to assess intrarater reliability. The video samples will be presented without audio to prevent bias of the participant's voice quality on the judges' ratings.

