The parameters to be evaluated are glottal closure (complete, anterior gap, posterior gap, hourglass, spindle gap, irregular, or incomplete), amplitude (magnitude of lateral movement of the vocal folds, in %), mucosal wave (magnitude of lateral movement of the mucous membrane in %), vertical level (on-plane, off-plane left lower, or off-plane right lower), nonvibratory portion (adydynamic segments of tissue that appear stiff, in %), anteroposterior (AP) and mediolateral (ML) supraglottic activity (constriction of the supraglottic structures, rated 0 – 5 with the aid of concentric circles), free edge contour (normal, convex, concave, irregular, or rough), phase closure (open phase predominates, nearly equal, or closed phase predominates), phase symmetry (the degree of symmetry between the left and the right vocal folds in terms of opening and closing, in %), and regularity (consistency of averaged stroboscopic cycles, in %) (Poburka et al., 2017).

STATISTICAL ANALYSIS PLAN

The data will be analyzed statistically by SPSS version 28 (SPSS Corporation, Chicago, IL, USA) at $\alpha = 0.05$.

To determine the interrater reliability of the visual-perceptual ratings, a two-way mixed, consistency, average-measures intraclass correlation coefficient (ICC) will be calculated for the continuous variables, and a Cohen's kappa (K) will be used for the nominal variables (Hallgren, 2012; Koo & Li, 2016). Intrarater reliability will be determined using a two-way mixed, absolute agreement, single-measures ICC for the continuous variables, and a Cohen's K will be used for the nominal variables (Hallgren, 2012; Koo & Li, 2016).

Linear mixed model analyses will be used to compare the groups over phonatory condition (habitual [u] phonation vs SOVT phonation) on each continuous variable using the restricted maximum likelihood estimation and scaled identity covariance structure. Group, Phonatory Condition and Phonatory Condition * Group interaction will be determined as fixed factors. A random intercept for subjects will be included. Model assumptions will be checked by inspecting whether residuals were distributed normally. Within-group effects of Phonatory Condition will be determined by posthoc pairwise comparisons. Marginal homogeneity tests will be used to compare nominal variables between habitual /u/ phonation and SOVT phonation within groups.

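### The nominal outcomes are tested only within each arm and never compared with the randomised control, so the planned tests cannot attribute a change to straw phonation

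*Combined protocol and SAP*

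**What the plan says.** The Design section sets up a randomised comparison: "Participants will be assigned randomly to one of three experimental groups or a control group". The control task is listed as "4) /u/ phonation with similar soft onset and slightly pursed lips as in SP but without a straw (control group". Under the heading on strobovideolaryngoscopy and phonatory tasks, the order is the same for everyone; participants "phonate an [u] vowel at habitual pitch and loudness (baseline), followed by the specific SOVT exercise of their group assignment".

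The Statistical Analysis Plan then divides the effect analyses by type of variable.

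- **Continuous:** "Linear mixed model analyses will be used to compare the groups over phonatory condition (habitual [u] phonation vs SOVT phonation) on each continuous variable". The model contains group, condition and their interaction. A within-arm step follows: "Within-group effects of Phonatory Condition will be determined by posthoc pairwise comparisons".
- **Nominal:** "Marginal homogeneity tests will be used to compare nominal variables between habitual /u/ phonation and SOVT phonation within groups". Nothing else is planned except Cohen's kappa, which measures rater reliability.

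The SAP does not list which parameters it treats as nominal. Judging by the rating categories under Visual-perceptual ratings, there are four: "glottal closure (complete, anterior gap, posterior gap, hourglass, spindle gap, irregular, or incomplete"), vertical level, free edge contour, and "phase closure (open phase predominates, nearly equal, or closed phase predominates").

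**The concern.** The control arm exists so that a change seen with the straw can be set against the change seen without it. Several things other than the straw differ between the habitual [u] and the exercise: the exercise always comes second, and it adds a soft onset and pursed lips. Adaptation to the laryngoscope between the two tasks is a further plausible influence, although the documents do not mention it. Control participants go through all of this too.

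For the nominal outcomes the plan tests each arm against its own baseline and stops there. A significant result shows that the distribution of categories differed between the two tasks in that arm. It does not show that straw phonation caused the difference. The SAP gives no rule for reading the four arm results together. The natural reading, significant in a straw arm but not in control, is not a test of a difference between arms. Any statement about the effect of straw phonation on closure pattern, vertical level, edge contour or phase closure would then lack the randomised comparison.

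**Working it through.** **Step 1. Text.** Setting the two analysis sentences side by side:

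| | Within-arm comparison | Between-arm comparison |
|---|---|---|
| Continuous variables | planned (post hoc) | planned (interaction) |
| Nominal variables | planned | none |

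Four nominal outcomes in four arms give 4 × 4 = 16 within-arm tests, and none against control. The conclusion rests on this step alone.

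**Step 2. Inputs for an illustration.** From the SAP: α = 0.05 (two-sided assumed). From the Design section: three straw arms and one control. Assumed, because the documents give no figures: 12, 15 or 20 per arm; a two-category outcome; the same proportion *s* shifting one way in every arm, from 10% to 50%; and 5% moving the other way. Straw phonation thus adds nothing.

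**Step 3. Within-arm test.** Let *b* and *c* be the numbers moving each way. The exact version refers *b* to a binomial distribution with *b* + *c* trials and probability 1/2. The asymptotic version uses z = (b − c)/√(b + c). The SAP does not say which will be run. Summing the multinomial probabilities of all significant outcomes gives *q*, the chance that one arm is significant.

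The reading of significant in straw, not in control, then has probability
- q(1 − q) for one straw arm, with maximum 0.25;
- (1 − q)[1 − (1 − q)³] for at least one of three straw arms.

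Exact version:

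| Shared shift | q, 12 per arm | q, 15 per arm | q, 20 per arm | One straw arm, 15 per arm | Any of three, 15 per arm |
|---|---|---|---|---|---|
| 10% | 0.0004 | 0.0014 | 0.0054 | 0.001 | 0.004 |
| 15% | 0.0033 | 0.0101 | 0.0318 | 0.010 | 0.030 |
| 20% | 0.0135 | 0.0363 | 0.0950 | 0.035 | 0.101 |
| 30% | 0.0802 | 0.1668 | 0.3212 | 0.139 | 0.351 |
| 40% | 0.2256 | 0.3776 | 0.5823 | 0.235 | 0.472 |
| 50% | 0.4201 | 0.5959 | 0.7847 | 0.241 | 0.377 |

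For example, at 30% and 15 per arm: 0.8332 × (1 − 0.8332³) = 0.8332 × 0.4216 = 0.351. The asymptotic version gives 0.47 in the same setting. Its *q* runs from 0.017 to 0.26 for shifts of 10–20% and from 0.31 to 0.86 for shifts of 30–50%.

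**Step 4. Between-arm test under the same assumptions.** Score each participant's change −1, 0 or +1. Compare a straw arm with control by the exact two-sided permutation distribution of the summed score, conditioning on the shared control's counts for the three-arm figures. False-positive rates over all shifts and arm sizes:
- one contrast at 0.05: 0.4–2.6%;
- any of three, unadjusted: 1.1–6.7%;
- any of three, Holm (smallest p ≤ 0.05/3): 0.1–2.2%.

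At 30% and 15 per arm, any of three is 5.5% unadjusted and 1.8% with Holm. The step from 35% to 5.5% comes from comparing with control; the step to 1.8% is multiplicity control.

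**Step 5. Where the illustration is weak.** With the exact version and a 10% shift, the one-arm pattern occurs in 0.04–0.5% of trials, no more often than the between-arm false positive (0.4–1.3%). It becomes more frequent from shifts of about 15–20% at 15–20 per arm, and from 30% at 12 per arm.

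**The case against.** The omission itself is not disputed, but its weight can be.

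- **The error is anticipated, not planned.** The SAP draws no conclusion from the nominal tests and states no rule for contrasting a significant straw arm with a non-significant control. The within-arm tests are valid for what they test, and the data would allow a between-arm test to be added. This stands: the fault lies in the planned analysis, not in the design or the data. But the tests are planned at α = 0.05 and nothing labels them descriptive.
- **The figures depend on assumptions.** The large values need 30–50% of control participants to change category, which nothing in the documents supports. The outcomes have 7, 3, 5 and 3 categories, so the two-category model is a simplification. Both points stand, and the figures show only what could happen.
- **Control does not isolate the straw in every arm.** The two water arms also add water and a cup. Contrasts there concern straw phonation in water as a whole. This affects wording, not the need for the comparison.
- **The choice of test is partly preference.** A multinomial or ordinal mixed model, or GEE with an interaction, would also serve. That is correct; what matters is that some between-arm test is prespecified.
- **The reach is limited.** No primary outcome is named, and variables treated as continuous get the randomised comparison. This stands and limits the seriousness.

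**Conclusion.** The concern holds. Followed as written, the plan never compares the nominal outcomes with the randomised control, so those tests cannot by themselves attribute a change to straw phonation. This rests on the text and needs no assumption beyond the reading that about four parameters are nominal.

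The size of the risk cannot be fixed from the documents. Under the stated assumptions and no straw effect, the misleading pattern across three straw arms ranges from 0.1% to 47% of trials, depending on the shared shift, arm size and version of the test. The matter should be corrected, but it is confined to conclusions about the nominal outcomes.

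**What to change.** 1. **Add a between-arm comparison for each nominal outcome.** Compare the habitual-to-exercise change in each straw arm with that in control, for example by an exact permutation test of the change score, with Holm adjustment over the three contrasts and no omnibus gate. A mixed model or GEE with the interaction is an option where cell counts allow.
2. **List the nominal parameters and state the scoring.** One workable choice is closure as complete or other, vertical level as on-plane or off-plane, and edge contour as normal or other, each with change −1, 0 or +1. Phase closure can stay ordered, with change −2 to +2. Report the full habitual-by-exercise table per arm so that shifts between gap types remain visible.
3. **Report each straw-minus-control difference in change** with a 95% confidence interval, and name the interval method.
4. **Base any straw-effect conclusion on this comparison**, and label the marginal homogeneity tests as within-arm description. The document is dated March 2023 and the participants come from the 2021–2022 academic year. If nominal data have already been seen, report the added test as post hoc.

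The minimum alternative is one sentence: the nominal results describe change within arms and support no conclusion about a straw effect.

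**Cost:** about one paragraph of SAP text and one analysis per nominal outcome, with no new data. Collapsing categories loses detail, and power is low in small arms. If 50% shift in each straw arm and 10% in control (5% the other way), the Holm-adjusted test finds at least one contrast in 41%, 55% and 71% of trials at 12, 15 and 20 per arm. A given contrast passes the first Holm step in 19%, 28% and 41%. These figures use the −1/0/+1 score and do not cover the ordered phase-closure score. Holm here covers the three contrasts within one outcome, not multiplicity across outcomes.

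### The SAP fixes neither the variant of the marginal homogeneity test nor the category codes; if SPSS's scored version is run, results for the three unordered ratings can depend on arbitrary numbering

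*Combined protocol and SAP*

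**What the plan says.** The first sentence of the Statistical Analysis Plan sets the software: "The data will be analyzed statistically by SPSS version 28", at a significance level of 0.05. Its last sentence is the whole plan for testing the categorical ratings: "Marginal homogeneity tests will be used to compare nominal variables between habitual /u/ phonation and SOVT phonation within groups".

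The parameter list that closes the protocol part contains four categorical ratings:

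- "glottal closure (complete, anterior gap, posterior gap, hourglass, spindle gap, irregular, or incomplete": seven types, with no natural order.
- "free edge contour (normal, convex, concave, irregular, or rough": five types, with no natural order.
- "vertical level (on-plane, off-plane left lower, or off-plane right lower": three types; the listed order is not a scale.
- "phase closure (open phase predominates, nearly equal, or closed phase predominates": three levels that do have an order.

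The reliability paragraph also treats ratings of this kind as nominal ("a Cohen's K will be used for the nominal variables"). Nowhere does the plan state which marginal homogeneity test is meant, what codes the categories receive, whether categories may be merged, or whether p-values are exact or asymptotic.

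**The concern.** Marginal homogeneity is a hypothesis that can be tested in more than one way. Stuart-Maxwell and Bhapkar compare all category proportions at once and ignore labels. The scored version assigns a number to each category and asks whether the mean number shifts between the two phonations. That is sensible for ordered levels. For unordered types the mean code has no meaning, and moves in different directions can cancel or reinforce each other according to the numbering.

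The SAP couples the bare test name with SPSS, where the paired procedure of that name is the scored one. If the analyst follows that route, a data-entry choice that the plan leaves open can decide whether a rating is reported as changed. This is the only inferential test that the SAP states for these ratings, and it is run separately in four groups ("Participants will be assigned randomly to one of three experimental groups or a control group"). Blinded rating gives no protection, because the choice arises after rating.

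**Working it through.** **Inputs.** Software, test name and categories come from the SAP and the parameter list. The documents give no group size, category frequencies or p-value, so there is no figure of the plan's to reproduce, and the tables below are hypothetical. Two-sided tests are assumed. That SPSS uses the scored statistic is knowledge of the software, not a statement in the documents.

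**Scored statistic.** For each student who changes category, d = (code under SOVT) − (code at baseline). Then z = Σd / √Σd². Students rated the same in both conditions contribute nothing. The exact p-value is the share of all sign patterns of the d values with |Σd| at least as large as observed.

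**Two categories among changers.** Every d is +c or −c. With a changes one way and b the other, z = c(a − b) / √(c²(a + b)), which is (a − b)/√(a + b) up to sign: McNemar without continuity correction, whatever the codes. Example: 8 posterior to complete and 1 back gives |z| = 7/√9 = 2.33, p = 0.020, exact p = 20/512 = 0.039 under every coding.

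**Vertical level: 4 students on-plane to left lower, 4 on-plane to right lower.**

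- Listed-order codes (on 1, left 2, right 3): Σd = 4(1) + 4(2) = 12, Σd² = 4(1) + 4(4) = 20, z = 12/√20 = 2.68. Normal p = 0.007; exact p = 2/256 = 0.008.
- On-plane in the middle (left −1, on 0, right +1): Σd = −4 + 4 = 0, z = 0. Normal and exact p = 1.00, although all eight changers left the on-plane category.

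**Glottal closure: 6 posterior to hourglass, 3 posterior to complete, 1 hourglass to posterior.**

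- Listed-order codes (complete 1, posterior 3, hourglass 4): Σd = 6(+1) + 3(−2) + 1(−1) = −1, Σd² = 6 + 12 + 1 = 19, z = −0.23. Normal p = 0.82; exact p = 1024/1024 = 1.00.
- Alphabetical codes (complete 2, hourglass 3, posterior 6): Σd = 6(−3) + 3(−4) + 1(+3) = −27, Σd² = 54 + 48 + 9 = 111, z = −2.56. Normal p = 0.010; exact p = 16/1024 = 0.016.

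**Code-invariant comparator.** Stuart-Maxwell uses the differences between the two margins and their covariance, with one category dropped. The exact version swaps the two conditions within each changer.

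- Vertical level, dropping on-plane: differences (−4, −4), variances (4, 4), covariance 0. χ² = 16/4 + 16/4 = 8.00 on 2 df, p = 0.018; exact swap p = 4/256 = 0.016.
- Glottal closure, dropping posterior: differences −3 (complete) and −5 (hourglass), variances 3 and 7, covariance 0. χ² = 9/3 + 25/7 = 6.57 on 2 df, p = 0.037; exact swap p = 44/1024 = 0.043.

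| Hypothetical table | Scored test, exact p, first coding | Scored test, exact p, second coding | Stuart-Maxwell, exact p, any coding |
|---|---|---|---|
| Vertical level | 0.008 | 1.00 | 0.016 |
| Glottal closure | 1.00 | 0.016 | 0.043 |

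Bhapkar's statistic is χ²/(1 − χ²/n), where χ² is the Stuart-Maxwell value. It increases with χ² for fixed n, so both orderings give the same exact swap p-value.

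**The case against.** The strongest objection is that the decisive premise is not in the documents. They name a hypothesis and a software package, not a statistic; an analyst could run Stuart-Maxwell or Bhapkar and have no coding problem. This stands, and it is why the point is conditional. What the documents do show is that the variant and the codes are unspecified.

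Second, small-sample approximation can be mistaken for code dependence. Take six changers: 5 posterior to complete and 1 complete to incomplete. Normal p-values are 0.59 with listed codes, 0.0495 with alphabetical codes, and 0.033 with complete coded 7 and the others 1 to 6 in listed order. The exact values are 54/64 = 0.84, 0.0625 and 0.0625, so the apparent crossing of 0.05 disappears. This also stands, and the case therefore rests on the two tables above, where the reversal survives exact calculation.

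Third, scope. A reader might infer that every unordered rating's result is affected. It is not: with two categories among changers the codes drop out, and if the two margins are identical z is 0 under any coding. Organic pathology is an exclusion criterion and both phonations occur in one examination, so vertical level and free edge contour may change little. That is plausible, but it is inference, and the plan cannot rely on it.

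Fourth, importance. These are within-group comparisons. The stated between-group comparison is the mixed model on the continuous ratings, which is untouched, and no primary outcome is named. This argues against calling the issue critical, not against settling it.

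**Conclusion.** The point holds conditionally. The SAP leaves open which marginal homogeneity test is used and how categories are numbered. If the SPSS scored test is run, p-values for glottal closure, free edge contour and vertical level can depend on arbitrary codes when changers span three or more categories. The tables show that exact p can move from 0.008 to 1.00, or from 1.00 to 0.016, on unchanged data. Phase closure is not affected if it is coded in its natural order.

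Two stronger readings are tempting. One is that the plan definitely prescribes an invalid test; the documents do not name the scored variant. The other is that a known share of the group-level results would turn on coding; any such percentage would need group sizes, baseline frequencies and change rates that the documents do not give. The examples prove that the dependence can occur, not how large it is here.

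The conclusion assumes the SPSS behaviour described and two-sided testing at 0.05. It should be fixed, but it does not threaten the mixed-model analyses.

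**What to change.** Replace the last sentence of the SAP with one that separates the ratings:

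- **Glottal closure, free edge contour, vertical level:** a code-invariant paired test (Stuart-Maxwell or Bhapkar) within each group, with the p-value from exact swapping of the two conditions within student, since changers per group may be few.
- **Phase closure:** the scored marginal homogeneity test may stay, with codes 1-2-3 in its natural order, from open to closed phase predominating.

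The cost is that sentence and a short script outside the SPSS menu. No new data or ratings are needed; if the tests have already been run, they can be repeated from the stored consensus ratings. If a code-invariant test was intended all along, the change only records it.

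### The within-arm marginal homogeneity test for seven-category glottal closure is unspecified: the asymptotic omnibus form is very conservative and loses power, and the score form depends on arbitrary category codes.

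*Combined protocol and SAP*

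**What the plan says.** The section Visual-perceptual ratings defines "glottal closure (complete, anterior gap, posterior gap, hourglass, spindle gap, irregular, or incomplete", which is seven unordered categories, and "free edge contour (normal, convex, concave, irregular, or rough", which is five. The Statistical Analysis Plan sets alpha at 0.05, names SPSS version 28, and gives one sentence on these variables: "Marginal homogeneity tests will be used to compare nominal variables between habitual /u/ phonation and SOVT phonation within groups".

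The Design section says "Participants will be assigned randomly to one of three experimental groups or a control group", so every nominal variable is tested four times, once per arm.

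The documents do not give:
- the form of the test (omnibus with up to k - 1 degrees of freedom, or score-based with 1);
- whether p-values are asymptotic or exact;
- a rule for empty categories or for collapsing categories;
- a total sample size, arm size, expected shift or power. On recruitment, the Participants section says only that students "will be recruited for this study by convenience sampling".

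**The concern.** An omnibus test of seven categories spends up to 6 degrees of freedom on the participants who change category within one arm. Those participants can fall in any of 7 x 6 = 42 off-diagonal cells. With few movers, the chi-square reference distribution is a poor approximation. If it errs towards conservatism, a real and consistent movement towards complete closure may fail to reach significance because the movers started from different gap patterns.

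A score-based test avoids the many degrees of freedom, but it needs a number for each category. These categories have no order, so the p-value then depends on an arbitrary numbering that the SAP does not fix.

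Either way, the result for closure pattern could turn on an unstated software choice, or on a decision made after the data are seen.

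**Working it through.** The plan gives no sample size or power figure, so there is none to reproduce.

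**Inputs from the documents.** Seven closure categories, four arms, alpha 0.05, paired comparison within arm.

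**Assumed inputs.** Category shares of 30/5/40/7/7/6/5% in listed order. Of the participants, 30-70% keep their baseline category and the rest are rated afresh from the same shares. Arm sizes are 12 to 60. For power, 50-70% of closures that would otherwise be incomplete become complete.

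**Expected movers with no true change.** The chance that two independent ratings differ is 1 - (0.30² + 0.05² + 0.40² + 0.07² + 0.07² + 0.06² + 0.05²) = 1 - 0.2684 = 0.7316. At 20 per arm:
- 70% tied: 20 x 0.30 x 0.7316 = 4.4 movers;
- 30% tied: 20 x 0.70 x 0.7316 = 10.2 movers.

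These are spread over 42 cells.

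**False-positive rate of the asymptotic omnibus (Stuart-Maxwell) test.** The statistic is X² = d'V⁻d, where d is the vector of differences in marginal counts, V⁻ is a generalised inverse of its estimated covariance, and df = rank of V. By simulation, against a nominal 5%:
- 12-25 per arm: under about 1%;
- 60 per arm: under about 3%.

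Separate simulations with other category distributions gave at most 0.9% at 8-30 per arm.

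**Power at 20 per arm, same assumptions:**

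| Test | Power |
|---|---|
| Asymptotic omnibus, seven categories | 17-52% |
| Omnibus, within-pair permutation p-value | 35-72% |
| Exact McNemar, complete vs not complete | 51-93% |

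At 30 per arm the asymptotic omnibus test reaches 43-88%.

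**Worked case.** Eight participants move to complete from five gap types (counts 2, 2, 2, 1, 1) and none move back. Leaving out the complete category, V is diagonal with the counts nᵢ, so X² = Σ dᵢ²/nᵢ = 2 + 2 + 2 + 1 + 1 = 8.
- Asymptotic omnibus: X² = 8 on 5 df, p = 0.156.
- Permutation omnibus: X² reaches 8 only if both movers in each group of two go the same way, so p = (1/2)³ = 0.125.
- Exact McNemar: p = 2 x (1/2)⁸ = 0.0078.
- Score-based: z = Σ(code difference)/√Σ(code difference²). Code complete as 1 and the five gap types as 7, 6, 5, 4, 3. The differences are 6, 6, 5, 5, 4, 4, 3, 2, with sum 35 and sum of squares 167, so z = 35/√167 = 2.71 and p = 0.007. Code complete as 4 and the gap types as 7, 2, 5, 1, 3. The differences are 3, 3, -2, -2, 1, 1, -3, -1, with sum 0, so p = 1.0. Over all assignments of codes 1-7, p is below 0.05 in 53%.

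**Limit of collapsing.** Exact McNemar needs at least six one-way movers: five give p = 0.0625 and six give p = 0.031. For a moderate shift (complete closure from 25-30% to about 54-57%), its power at 10 per arm is only 3-5%.

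**The case against.** **The SAP does not name the omnibus test.** This is correct. With categories coded in listed order, the 1-df score version has 48-89% power at 20 per arm, close to exact McNemar. But no order is defined for these categories, and the worked case shows p running from 0.007 to 1.0 as the codes change. Its power is therefore no defence of leaving the version open.

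**The worked case is a diluted pattern.** This also stands. Under the omnibus test, eight movers from a single gap type give p = 0.005, and from two types p = 0.018 (X² = 8 on 1 and 2 df). The example shows how the test can fail, not how often.

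**Exact McNemar is conservative too.** Under the same null it rejects 0-1.7% at 12-25 per arm and at most 3.1% at 60. Its advantage is power for a shift in completeness, not better calibration. It also discards gap-type information, so it should be added beside the seven-category test and not substituted for it.

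**Stronger readings a reader might infer.**
- That the planned test has almost no chance of detecting a change. This is not general. It fits an omnibus test with about 15 or fewer per arm and small to moderate shifts (power at most about 12%), but not 30 per arm with a large shift (77-85%, complete closure rising from 25-30% to about 69-71%). The documents give neither arm size nor shift.
- That the statistic often cannot be computed. That arises only if a full-rank matrix is required. With a generalised inverse and df equal to the rank, the problem disappears.
- That closure has priority because it is listed first. The parameter list is unranked and no primary outcome is designated.

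**Conclusion.** The point holds as a specification gap with a measurable cost. If the planned test is the asymptotic omnibus one, it runs far below its nominal 5% at every arm size examined from 12 to 60. At 20 per arm it also gives up a large part of the available power for a shift towards complete closure. If it is the score-based one, the p-value depends on arbitrary codes. Neither is a sound default for unordered categories.

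The sizes rest on assumed arm sizes, category shares, tied fractions and shifts. The simulations cover glottal closure only. Free edge contour, with five categories (up to 4 df), shares the mechanism but was not simulated.

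Few movers in small arms are part of the cause, and no choice of test removes that. The documents do not say that a non-significant result would be reported as no change, but such a result from this test could not support that reading.

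**What to change.** Amend the Statistical Analysis Plan to state:

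1. Multi-category nominal variables are tested within arm by the omnibus marginal homogeneity statistic, not a score-based one. P-values come from the exact or Monte Carlo within-pair permutation distribution (exchanging the two conditions within each participant). Name the procedure, and confirm that it produces this statistic.
2. For glottal closure, complete versus any incomplete pattern is the pre-specified focused contrast, tested by exact McNemar within arm. The seven-category permutation test is kept as supportive.

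The cost is SAP wording and slight extra computing. The downside is that shifts between gap types that leave completeness unchanged are covered only by the less powerful seven-category test. Fixing the contrast in advance also prevents categories being collapsed after the data are seen. It does not make arms of about 10 adequate, so the planned arm size should be stated beside it.
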